To maintain stability in patients with schizophrenia requires effective self-management of symptoms and consistent treatment adherence. Perhaps the most notable period in the continuum of care when coping and medication/appointment adherence are jeopardized is during the first months following discharge from acute hospitalization. Various factors associated with adherence have been described in our pilot work, and we have used these data to inform the development of a theoretically- and empirically-grounded, mobile intervention app following hospitalization, which we are currently in the process of developing. We will test the feasibility, acceptability, and potential effectiveness of our mobile app, that we call Mobile After-Care Support (MACS), to improve the target mechanisms of active illness self-coping and medication/appointment adherence post-hospital discharge. We plan to compare the MACS app to an attention-matched app that will assess variables of interest and provide non-adaptive information (i.e., education) in the context of a RCT design for patients recently hospitalized for psychosis. To aid in app development and planning, we will also conduct qualitative interviews of clinical stakeholders regarding their perspectives on the app.

C. Experimental Method

C1. Brief Description of Subjects

Study A. Participants in this study will consist of 80 patients diagnosed with schizophrenia-spectrum disorders who have been hospitalized for acute psychiatric reasons at Butler Hospital. See detailed inclusion/exclusion criteria below.

Study B. We also will select 20 clinical stakeholders for participation. These participants will be selected from clinicians, administrators, and support staff working at Butler Hospital, The Providence Center, and other mental health programs in the area. We do not propose recruiting a specific number of each group at this point. As is typical of qualitative methods, we will interview stakeholders until we have reached saturation on relevant themes. Therefore, the numbers for each type of stakeholder recruited will vary; although we will attempt to interview several for each category. See detailed inclusion/exclusion criteria below.

C2. Study Design

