Study A. We will use the pilot RCT ($n = 80$) to assess MACS acceptability/ feasibility and its preliminary effectiveness relative to a control condition. Randomization will be used to help ensure balance among treatment conditions. We will stratify by diagnosis (schizophrenia/schizopreniform vs schizoaffective) and by gender (male vs female). We will conduct randomization using a computer generated list via REDCap held by a staff person no otherwise affiliated with the study. We will review patient acceptability/ satisfaction ratings and ease of use of mobile devices as measured by the CSQ-8 and patient qualitative interviews. These data will inform further refinements of the MACS app that will be used in future research.

Study B. We also will conduct 30-minute individual interviews of clinical stakeholders ($n = 20$). Interviews will be led by members of the investigator team and a study research assistant (RA) listening to the conversation and taking notes. Interview agendas will be developed so that participants will receive similar types of questions, as well as those that may be specific to their job responsibilities (e.g., clinician vs administrator).

C3. Specific Procedures or Treatments

MACS Protocol. We will use an established mobile software service (ilumivu.com) which provides a secure platform (Android or Apple IOS compatible) that can be programmed to administer the MACS app. It does not require a high degree of IT support and allows for tailoring of content without the need for trained programmers. Further, we chose a mobile app that works with most smartphones, is easy to download/install, and runs largely autonomously. Because we are using a flexible software platform to deliver our mobile intervention and not a static app specifically designed for this project, we have flexibility to make changes to the content of the app during the project in an iterative fashion based on what we learn from the data being collected. In addition, future implementation of the app can take advantages of ongoing improvements and updates to the platform that will be used in future iterations of our app-based interventions that would be proposed for a next step full-scale RCT if this project is successful.

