
Table 1. Traditional Assessments

	Construct assessed	Method	Time
Structured Clinical Interview for DSM-5 (SCID-5; Psychotic, Mood, Substance Use Modules) ⁵⁵	Axis I diagnosis	Interview	Baseline (BL)
Mini-Mental State Exam (MMSE) ⁶³	Cognitive functioning	Interview	BL
Phone Usage Questionnaire (PUQ)	Phone use	Self-Report	BL
Medication Event Monitoring System (MEMS) ⁴⁵	Medication adherence	Objective	1,2,4
Antipsychotic Medication Beliefs and Attitudes Scale (AMBAS) ⁶⁵	Medication beliefs	Self-report	BL,1,2,4
Brief Adherence Rating Scale (BARS) ⁵⁹	Medication adherence	Interview	BL,1,2,4
Treatment History Interview-4 (THI-4) ⁵⁰	Appointment adherence	Interview	BL,1,2,4
Outpatient chart/medical records review	Treatment utilization	Objective	BL,1,2,4
Maastricht Assessment of Coping Strategies (MACS-II) ^{51,52}	Coping skills	Interview	BL,1,2,4
Brief Coping Orientation to Problems Experienced (COPE) ⁶²	Coping skills	Self-Report	BL,1,2,4
Brief Psychiatric Rating Scale (BPRS) ⁵⁶	Psychiatric symptoms	Interview	BL,1,2,4
WHO Disability Assessment Sched. 2.0 (WHODAS-2) ⁴⁰	Functioning	Self-Report	BL,1,2,4
Alcohol Use Disorders Identification Test (AUDIT) ⁴²	Alcohol use	Self-Report	BL,1,2,4
Drug Use Disorder Identification Test (DUDIT) ⁶⁴	Drug use	Interview	BL,1,2,4
Usefulness, Satisfaction, and Ease of Use Questionnaire (USE) ⁶¹	Acceptability	Self-Report	1,4
System Usability Scale (SUS) ⁶⁰	Acceptability	Self-Report	1,4
Client Satisfaction Quest.-8 (CSQ-8) ⁵⁷	Acceptability	Self-report	1,4

Date most recently revised 6/14/2021

Protocol Version 1.9

End of Treatment Interview	Feedback	Interview	1,4
----------------------------	----------	-----------	-----

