We will use effect size changes to describe differences between groups over the time points on target mechanisms (adherence and coping), primary outcomes (overall symptom severity), and secondary outcomes (functioning, rehospitalization rates). We will calculate 95% confidence intervals (CIs) and clinical significance statistics (e.g., NNT). Because CIs will likely be large, these analyses may not permit definitive conclusions. Given the limitations and goals of pilot studies, we hope to build our case for future research by focusing primarily on the feasibility/acceptability of MACS and of the randomized design and the clinical significance of effects compared to our mobile attention control. Some parameters estimated in the pilot study (e.g., stability of outcome measures across time) may be helpful for informing estimates for a large scale, adequately powered RCT. Secondarily and consistent with analyses we would conduct in a future full-scale RCT, we will generate multilevel models to examine whether treatment condition, time, and the treatment condition X time interaction predicts change in outcomes (symptoms, functioning, re-hospitalization) and proposed mechanisms. Generalized estimating equations will be constructed to examine differences in rehospitalization rates over time. We will assess whether the groups differ on covariates at baseline (e.g., demographics) and, if so, include them in the statistical models. Given the smaller sample size, we will examine changes in mediators over time across conditions and correlations between mediators and outcomes, which are pre-requisites for formal mediation. We also will examine outcome predictors (e.g., baseline adherence) to identify possible moderators to test in future studies

Qualitative interviews will be recorded and the interviewer will keep notes of the conversation. The MPIs will develop an initial codebook with deductive codes. Then inductive codes capturing emergent themes will arise from team-level review of interviews. Once codes are developed, the research team will independently code remaining transcripts; 20% of transcripts will be double coded and reviewed to ensure inter-rater reliability. The MPIs will perform thematic analysis in which the passages assigned to codes will be read in aggregate to identify key themes.

C5. Videoconferencing

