Due to COVID-19 restrictions and recent developments in the use and popularity of telehealth, we also will offer participants the ability to complete study assessment sessions by secure videoconferencing per current CNE policy (e.g., HIPAA-compliant Zoom). Participants will be informed of the potential risks and limitations of videoconferencing related to confidentiality issues in the consent form. Participants who do not have or want to use videoconferencing will still be able to complete study assessments over the phone.

D. Material Inducements

For Study A, we will compensate patient participants for completion of in-person assessments \$30 each at the baseline, 1, 2, and 4 month follow-ups, with an additional \$10 increase for each consecutive follow-up completed (i.e. if all appointments are completed, patient participants will be compensated \$30, \$40, \$50, and \$60 at each timepoint, for a possible total of \$180). Patient participants who are found to be ineligible for the study following administration of the SCID (used to determine/confirm diagnosis) will be compensated \$15 for their time (half of the full baseline compensation amount). Patient participants will be compensated an additional \$20 for returning the electronic pill caps or a borrowed study phone, if applicable, for up to \$200 total. For completion of mobile surveys during the first month post-discharge, patient participants will be compensated \$0.25 per completed app session up to three per day (for a possible total of \$22.50). In total, patient participants can be compensated up to \$222.50 for their participation. For Study B, we will compensate stakeholder participants \$50 for completion of the interviews.

E. Training of Research Personnel

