The research assistants (RAs) will be directly supervised by Drs. [name] and [name]. All RAs in the psychosocial treatment program undergo extensive training in screening medical records (including the appropriate permissions to access electronic medical records), approaching patients on the units, obtaining consent to participate, collecting and entering data, and maintaining confidentiality. All RAs have received training in the informed consent process and their ethical responsibilities when conducting research. Additionally, all RAs will receive specific training in the assessment instruments to be administered. Drs. [name] and [name] also will train and supervise the master's level clinician who will meet with patients for the initial app session before discharge and send brief reports during the study to patients' community clinicians based on assessment data collected.

3) Human Subjects

A. Subject Population

Study A. Participants in this study will consist of 80 patients diagnosed with schizophrenia-spectrum disorders who have been hospitalized for acute psychiatric reasons at Butler Hospital.

Inclusion criteria are: (1) currently hospitalized in inpatient or partial hospitalization; (2) DSM-5 criteria for schizophrenia, schizoaffective, schizophrenia unspecified/other, or mood disorder with psychotic features (bipolar or major depressive disorder) specified based on the Structured Clinical Interview for DSM-5⁵⁵ (SCID-5); (3) 18 years or older; (4) prescribed oral psychotropic medication upon discharge; and (5) ability to speak and read English (materials written at a 5th grade reading level). Exclusion criteria are: (1) planned discharge to

supervised living setting or participation in formal outpatient adherence programs (e.g., medication packaging) or (2) pregnancy or other medical condition (e.g., dementia as indicated by patients' medical charts) contraindicating use of antipsychotic medications.

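### The diagnosis stratification factor has no level for mood disorder with psychotic features, which inclusion criterion 2 admits, and the analysis section does not close the gap

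*Combined protocol and SAP*

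**What the plan says.** Section C2 (Study Design, Study A) sets two stratification factors: "We will stratify by diagnosis (schizophrenia/schizopreniform vs schizoaffective) and by gender (male vs female" (the spelling is the protocol's). Allocation is from a computer-generated REDCap list.

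Section 3, Subject Population, inclusion criterion 2 requires "DSM-5 criteria for schizophrenia, schizoaffective, schizophrenia unspecified/other, or mood disorder with psychotic features (bipolar or major depressive disorder", established by the SCID-5. Table 1 schedules the "Structured Clinical Interview for DSM-5 (SCID-5; Psychotic, Mood, Substance Use Modules" at baseline. Section D (Material Inducements) provides for patients "found to be ineligible for the study following administration of the SCID (used to determine/confirm diagnosis", so the diagnosis is known at entry.

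On covariates, section C4 (Data Analysis) says "We will assess whether the groups differ on covariates at baseline (e.g., demographics) and, if so, include them in the statistical models". It also warns: "Because CIs will likely be large, these analyses may not permit definitive conclusions".

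**The concern.** A stratified scheme needs every eligible patient to belong to exactly one stratum. Here the factor in C2 and the eligibility criterion in section 3 are both current text, and they do not describe the same set of diagnoses. Nothing else in the protocol maps the eligible diagnoses to levels, adds a level, or limits stratification to a subset of patients.

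Two things follow. The rule cannot be applied from the text to a patient with a psychotic mood disorder. And the split of that group between arms is left to chance, although diagnosis was thought important enough to stratify on.

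The analysis could have made up for this by adjusting for diagnosis. C4 instead makes adjustment depend on an observed baseline difference, gives no criterion for a difference, and names neither stratification factor. Its list of examples is open, so the factors are not excluded, but their inclusion is not assured and the model depends on the data.

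This matters somewhat more in a pilot that lists the feasibility of randomization among its aims (Aim 1b) and offers its models as those of a future full-scale trial.

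**Working it through.** **Step 1. Compare criterion 2 with the factor.**

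| Diagnosis in criterion 2 | Level in C2 |
|---|---|
| Schizophrenia | First level |
| Schizoaffective | Second level |
| Schizophrenia unspecified/other | None named; the first level is plausible but not stated |
| Mood disorder with psychotic features | None |

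Two of the four groups are named, one fits by interpretation, and one has no level.

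**Step 2. Size of the precision effect.** The protocol gives no figure to reproduce: it states no mood-disorder share, allocation ratio or diagnosis effect. Assume N = 80 (from the protocol), 40 per arm, no loss to follow-up, m = 8 to 24 mood-disorder patients (10% to 30%), allocation without regard to that group, and a mean outcome difference d (in SD units) between that group and the rest.

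- Number k of the group falling in one arm: Var(k) = m(80 − m)/(4 × 79). For m = 8: 8 × 72/316 = 1.823. For m = 24: 24 × 56/316 = 4.253.
- Between-arm difference in the group's proportion: SD = 2√Var(k)/40, giving 0.068 (m = 8) and 0.103 (m = 24).
- SE of the arm contrast with perfect balance: √(2/40) = 0.2236 SD.
- SE without balance or adjustment: √(0.05 + d² × SD²). For d = 0.5 and m = 8: √(0.05 + 0.25 × 0.00456) = 0.2261. For m = 24: √(0.05 + 0.25 × 0.01063) = 0.2295.

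| m (share) | SD of difference in proportions | SE increase, d = 0.25 | d = 0.5 | d = 0.8 |
|---|---|---|---|---|
| 8 (10%) | 0.068 | 0.3% | 1.1% | 2.9% |
| 12 (15%) | 0.080 | 0.4% | 1.6% | 4.0% |
| 16 (20%) | 0.090 | 0.5% | 2.0% | 5.1% |
| 24 (30%) | 0.103 | 0.7% | 2.6% | 6.6% |

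**Step 3. Cost of adjusting.** With r the chance correlation between arm and group membership, adjustment multiplies the variance by 1/(1 − r²). Its mean over the hypergeometric distribution of k is about 1.013 for each m, and √1.013 gives about 0.7% on the SE. Adjustment gains precision only when d exceeds √(0.0131 × 0.05/SD²): 0.38 at m = 8, falling to 0.25 at m = 24. Three diagnosis groups plus gender use 2 + 1 = 3 degrees of freedom. Going from 78 to 75 moves the 97.5% t quantile from 1.9908 to 1.9921, or 0.06%.

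**Step 4. Would imbalance be visible?** With 8 such patients, a 6:2 split or worse occurs in about 26% of allocations. With 12, 9:3 or worse occurs in about 11%. Either could bring C4's undefined rule into play.

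**The case against.** **Size.** This is a pilot focused on feasibility and acceptability, and it already concedes wide intervals. An SE change of 1% to 3% alters no conclusion. The calculation is also for a contrast at one time point, whereas C4 plans effect-size changes and condition-by-time models. A diagnosis difference in level that is stable over time cancels from change, so the figures then overstate the effect. Both points stand.

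**Covariates.** Selecting covariates by observed baseline difference would be open to criticism even if the strata matched criterion 2, and adjustment brings little net precision. That is fair. The reason to prespecify is to fix the model in advance. It also covers the mood-disorder group if that group is mapped into an existing level, since mapping alone does not balance it.

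**A rule may exist elsewhere.** The REDCap set-up is not shown and may contain a mapping. If so, the remedy is to copy it into C2.

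**Stronger readings that the documents do not support.**
- A reader might infer that the comparison is biased. It is not, provided the stratum rule is fixed before each allocation.
- A reader might infer that the list holder classifies diagnoses case by case, or that concealment is compromised. C2 says only that someone outside the study holds the list; it does not say who assigns the stratum.
- A reader might see a second contradiction because schizophreniform is a stratum label but is not named in criterion 2. It may be meant under unspecified/other.
- A reader might take the description "80 patients diagnosed with schizophrenia-spectrum disorders who have been hospitalized for acute psychiatric reasons" as a third conflict. Section C1 refers the reader to the detailed criteria, and in section 3 they follow directly, so this is only wording.

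**Conclusion.** The mismatch is established from the text alone: the stated stratification rule cannot place every eligible patient, and C4 does not ensure adjustment for the factor. The case rests on that conflict and on the ease of repair; validity is not threatened.

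Priority is minor to moderate. The SE effect of about 1% to 3% assumes a 10% to 30% mood-disorder share, 40/40 arms, no loss to follow-up and a 0.5 SD difference. Across differences of 0.25 to 0.8 SD it runs from 0.3% to 6.6%. The sample size of 80 is not affected.

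**What to change.** 1. **C2.** State the stratum for every eligible SCID-5 diagnosis, including mood disorder with psychotic features and unspecified/other, and schizophreniform if it is eligible. Apply this to patients still to be randomised. Enrolment status is not stated, but the text is Version 1.9 and its remote-recruitment section speaks of continuing record review, so some patients may already be allocated. For them, document the rule that was actually used; their allocations stand.

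2. **C4.** Prespecify SCID-5 diagnosis group (schizophrenia, schizophreniform and unspecified/other together; schizoaffective; mood disorder with psychotic features) and gender as covariates in the outcome models, in place of inclusion conditional on an observed baseline difference. Set in advance a rule for collapsing diagnosis groups in the rehospitalization GEE if events are sparse, because a small mood-disorder term may not be estimable there.

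**Cost.** A mapping sentence, a covariate sentence with the collapsing rule, and a short record of past practice. No new data are needed, because the SCID-5 is already done at baseline. The statistical price is about 0.7% of the SE and three degrees of freedom, with a small net loss of precision if the mood-disorder group differs by less than about 0.25 to 0.38 SD.

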Mobile Software Service. We will use an established mobile software service (ilumivu.com) which provides a secure, HIPAA-compliant application (Android or Apple IOS compatible) that can be programmed to administer the MACS app and the attention control app. Responses will be uploaded when internet/cellular access is available to a web portal for remote access/downloading from a convenient web portal interface. Otherwise, responses are stored on the native app in an encrypted format until uploading can occur. App updates and fixes can also be sent remotely to the app when needed. Raw app data will not be automatically sent to providers. Instead, staff will review mobile data weekly to monitor safety and contact patients if safety risk is detected. Patients will be informed that mobile data will not be reviewed in real time and that they should contact providers/seek immediate help if needed. These risk data will also be included in the periodic reports that are sent to providers. Patients will be prompted by the device to contact a crisis hotline, their providers (numbers pre-programmed into the device), or 911/local hospital if they report an immediate safety risk.

Mobile Device Training/Support. For individuals in both conditions, after obtaining consent at hospitalization (baseline), a research assistant will help patients install the app on their own smartphone when possible for convenience. If a patient is unwilling to install the app or does not own a compatible smartphone, we will supply a dedicated mobile device to the participant for this purpose post-discharge and they will return the device at the end of the study. Patients will practice responding to app sessions to familiarize themselves with the program and troubleshoot technical problems. Patients will be instructed to contact the study if questions arise post-discharge about using the device. For individuals in the MACS condition only, we also will employ a master's level clinician to meet with participants to review their discharge plan prior to leaving the hospital and discuss how to use the app to support their aftercare. For both conditions, app training/support meetings will be held prior to discharge when possible. If a patient is unexpectedly discharged, participants will be asked to return to our clinic, and this meeting will be held as shortly after discharge as possible, or it will be conducted over the phone if the participant is unable to return to the clinic.

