Clinical Outcomes and Other Measures. In addition to target mechanisms, we will assess clinical outcomes including: a) symptom severity (primary outcome), b) functioning, and c) re-hospitalization rates. a) We will use the BPRS,⁵⁶ a well-established interview measure of overall psychiatric symptom severity, including positive/negative psychotic symptoms, as well as mood symptoms and suicidality; b) the WHODAS-2^{39,40}, which is a brief self-report measure of functional impairment; and c) rehospitalizations obtained from the THI-4⁵⁰ as described above (and cross-checked with patients' medical records). In addition, the THI-4 will also be used to quantify overall treatment utilization, including the type and amount of mental health treatment received over follow-up (medications, psychosocial, hospitalizations, pharmacotherapy visits, ER visits, crisis calls, support groups). We also will administer the AUDIT/DUDIT, which measure alcohol/drug use and severity^{42,58,64}. The MMSE⁶³ will be used to assess cognitive functioning at baseline in order to describe patients' baseline characteristics and to examine this variable as a potential predictor of treatment response in our analyses. The AMBAS⁶⁵ is a brief self-report measure of medication beliefs. Acceptability/satisfaction with the mobile apps will be assessed using an adapted version of the CSQ-8⁵⁷ at the end of the study. Finally, participants will complete an end-of-treatment interview in which they will be asked what they liked and did not like about the app and study participation.

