After obtaining consent, the RA then will proceed to conduct the baseline assessment over the phone to confirm eligibility. We will follow all study safety procedures as previously outlined in the protocol. If entered into the study, all subsequent study procedures will be conducted remotely, including initial orientation of the study app (i.e., the participant will be given training and instructions for how to download and use the app on their smartphone) and follow-up assessments.

Study B. We will consult with our investigator team to identify appropriate clinical stakeholders to approach about study participation. Once identified, Drs. [name] or [name] or another member of the research team will contact the stakeholder directly to introduce the study. If interested and the interview is done in person, the participant will review and sign the consent form. They will be given a copy for their records. If the interview is done over the phone, the participant will be sent a copy of the consent form prior to the interview. Then the person will be consented over the phone. The consent process will be audiorecorded as documentation of consent. The participant will also be asked to return a signed copy of the consent form and to keep a copy for their records.

C. Potential Risks

Potential risks of study participation include: coercion, clinical deterioration/suicidality, loss of confidentiality/privacy, and adverse events (see details below).

D. Protection of the Subject

D1. Measures to Minimize Potential Risks

Coercion

Risks. The risk of potential coercion is judged to be minimal.

Minimization. The risk of coercion will be minimized by following standard procedures for obtaining informed consent. We will fully explain the study procedures, risks, benefits, and alternatives to all patients. Also, patients who do not consent or who withdraw at any time will receive usual clinical treatment with no prejudice. Additionally, participant remuneration will be set at modest monetary levels as used in similar studies, including our pilot work. We will obtain permission from the patient's treating physician to ensure that approaching the patient for research participation is clinically appropriate. We will stress that the decision by stakeholders about whether to participate in the study will not affect their employment status.

Risk of clinical deterioration/suicidality

Risks. In this type of population, the risk of clinical deterioration is present.

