Drs. [name] and [name] will have responsibility for day-to-day monitoring of the quality of operations in all data collection. There are several sources of data. Research participants will complete questionnaires. Research assistants also code all data from research interviews. Only the participants' study identification number will appear on any of the final paper data collection instruments. Finally, the audio recordings will be recorded onto a dedicated device. The recordings will be downloaded after the interviews onto secure servers and the files will be deleted from the devices. The recordings will be transcribed and the audio files will be destroyed after study completion. A study ID will be used to identify the recordings. Otherwise, they are not connected with the primary study database in any way.

This study will use Care New England's instance of REDCap for the collection and storage of data. The study will not collect or store any actual data within REDCap until the project has been moved into REDCap's production environment. REDCap is a secure, web-based application developed by Vanderbilt University for building and managing surveys and databases. It is primarily designed to support online or offline data capture for research studies, quality improvement, and operations. REDCap provides easy data manipulation (with audit trails for reporting, monitoring and querying patient records), real-time data entry validation, and an automated export mechanism to common statistical packages. Care New England's instance of REDCap is hosted within the Care New England data center in Warwick, RI. This REDCap instance is role-based and is fully integrated with CNE's Active Directory structure. It enjoys 24/7/365 enterprise-level support and security inherit to CNE's HIPAA-compliant data center. Network transmissions (data entry, survey submission, and web browsing) to and from REDCap are protected via TLS 1.2 encryption. REDCap's data is stored on encrypted servers within CNE's data center. The REDCap Consortium is composed of thousands of active institutional partners in over one hundred countries who utilize and support REDCap. REDCap was developed specifically around HIPAA-Security guidelines, and more information about the consortium and system security can be found at <http://www.projectredcap.org/>.

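### No assessor masking is specified for the interviewer-rated primary outcome (BPRS) or the other follow-up interviews, and the staff roles in the plan leave room for unmasked rating

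*Combined protocol and SAP*

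**What the plan says.** **Outcome.** C3, Clinical Outcomes and Other Measures, lists "symptom severity (primary outcome") first among the clinical outcomes and measures it with the BPRS, "a well-established interview measure of overall psychiatric symptom severity". Table 1 schedules the BPRS at baseline and months 1, 2 and 4. The MACS-II (coping), the THI-4 (appointments, rehospitalization) and the BARS (reported missed doses) are also interviews at those times.

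**Staff roles.**
- C3, Mobile Device Training/Support: for both conditions, "a research assistant will help patients install the app on their own smartphone". Practice sessions and troubleshooting are part of this step.
- 2E, Training of Research Personnel: "all RAs will receive specific training in the assessment instruments to be administered". No separate assessor group is described.
- 3.D3, Data management and protection: "Research assistants also code all data from research interviews".
- 3.B, Remote Recruitment Procedures: "the RA then will proceed to conduct the baseline assessment over the phone to confirm eligibility".
- C3 (MACS Protocol) and 3.D3 (Suicidality) have research staff review app data weekly. 3.D1 gives that review to the study clinician.
- 3.B, Study A: the study team checks in with participants from time to time to prompt app use.

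**Contact with app content at visits.** Table 1 places the "End of Treatment Interview" at months 1 and 4. It asks what patients liked and disliked about the app.

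**Safeguards present.** C2 has an unaffiliated staff member hold the randomization list. C4 has 20% of transcripts double coded, in the paragraph on qualitative interviews.

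**The concern.** An interviewer-rated symptom scale depends on the rater's judgement. A rater who knows the arm may score to expectation without intending to. The two apps ask the same questions and then differ in what they deliver (C3, Mobile App Attention Control Protocol), so anyone who installs, demonstrates or troubleshoots one can learn the arm. Neither safeguard addresses this. Holding the list elsewhere conceals upcoming assignments but does nothing for ratings made after assignment, and the double coding does not cover the BPRS.

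C4 plans between-group effect sizes with 95% CIs, NNT, multilevel models, and correlations between mediators and outcomes, and says some pilot parameters may inform a full-scale trial. If one unmasked interviewer rates both coping (MACS-II) and symptoms (BPRS), a shared expectation could shift both effect sizes and also contribute to the correlation between them, which Aim 1(e) examines. A wide confidence interval conveys sampling error; it gives no sign of rater bias.

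**Working it through.** **Step 1: is masking stated anywhere?** C2, C3, C4, 2E and 3.D3 are where it would be expected. None says that follow-up raters are masked, that assessment and app support are kept apart, or that guesses of arm are recorded.

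**Step 2: do the assigned roles protect masking by default?** Set side by side:

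| Task | Who, according to the protocol | Can it reveal the arm? |
|---|---|---|
| App installation and training | A research assistant (C3) | Yes, the app content differs |
| Weekly app-data review | Research staff (C3, 3.D3) or study clinician (3.D1) | Possibly |
| Prompting app use | Study team (3.B) | Possibly |
| App feedback interview, months 1 and 4 | Not named (Table 1) | Yes, if app content is described |
| Coding of interview data | Research assistants (3.D3) | Not applicable |
| BPRS at months 1, 2 and 4 | Not named; all RAs are trained | Not applicable |

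The overlap exists at the level of the role. Nothing keeps one person from doing both kinds of task for a patient, and nothing says that one person will. Baseline ratings are of less concern: in the remote procedure the baseline assessment confirms eligibility, so it plausibly precedes randomization, although the order is not stated.

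**Step 3: how large could the effect be?** The protocol gives no alpha, power, SD or expected effect for n = 80, so there is no figure of its own to reproduce. The following is an illustration.

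From the documents: n = 80 (Aim 1) and 95% CIs (C4). Assumed: 1:1 allocation, so 40 per arm; SD = 1; a two-sided 5% two-sample t-test at one time point; no true effect; a rater shift b of 0.1, 0.2 or 0.3 SD; and, as a second case, 20% dropout, so 0.8 × 40 = 32 per arm.

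Formulas, with m per arm:
- Standard error = √(2/m): √(2/40) = 0.224 and √(2/32) = 0.250.
- 95% CI half-width = 1.96 × standard error: 0.438 SD and 0.490 SD.
- Non-centrality δ = b / standard error, with 2m − 2 = 78 or 62 degrees of freedom.
- Rejection rate = P(|T| > critical value), with T non-central t with parameter δ.

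| Assumed shift b | δ, 40 per arm | Rejection rate, 40 per arm | δ, 32 per arm | Rejection rate, 32 per arm |
|---|---|---|---|---|
| 0.1 SD | 0.447 | 7.3% | 0.40 | 6.8% |
| 0.2 SD | 0.894 | 14.3% | 0.80 | 12.4% |
| 0.3 SD | 1.342 | 26.3% | 1.20 | 21.9% |

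A normal approximation gives nearly the same values at 40 per arm (7.3%, 14.5%, 26.9%). A 0.2 SD shift is 0.2/0.438 = 46% of the CI half-width at 40 per arm.

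The shift can also run against the intervention. By the normal approximation at 40 per arm, a true effect of 0.5 SD has 61% power without bias, 88% with a shift of +0.2 SD and 27% with a shift of −0.2 SD.

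**The case against.** The strongest reply is that the protocol is silent rather than unmasked. It mentions several RAs, so it could be followed to the letter with one RA setting up the app and another rating that patient. The sentence on RAs coding interview data sits in a data-management section, where coding need not mean rating. The remote procedure names nobody for app orientation. All of this stands. A reader might infer that the primary outcome will be rated by someone who knows the arm; the documents do not support that, because no section names the follow-up BPRS rater.

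A reader might also infer that the month 1 app questionnaires unmask the rater. The CSQ-8, USE and SUS are self-report, so a rater need not hear the answers, and the text places the CSQ-8 at the end of the study whereas Table 1 has months 1 and 4. Only the feedback interview is a plausible route, and its interviewer is not named.

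Other points limit the exposure. Both arms use an app on the same platform with the same assessment items and prompt frequency, so a passing mention of the app does not identify the arm. The MACS-only session on using the app for aftercare is led by a master's-level clinician. A claim that every target mechanism would be biased goes too far: medication adherence is measured by MEMS with pill-count back-up, adherence reports are checked against outpatient records, and the Brief COPE is self-report. A claim that effects would be inflated also goes too far, since bias can run either way.

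Finally, C4 puts feasibility and acceptability first and warns that conclusions may not be definitive. That lowers the consequence but does not remove it, because effect estimates are still planned and the feasibility of the assessments is itself part of Aim 1.

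**Conclusion.** The concern holds as an omission that matters: masking of follow-up raters is unprotected for the primary outcome and for the MACS-II, BARS and THI-4 interviews, and the roles as assigned permit unmasked rating. The documents do not establish that masking is broken. The results most exposed are the BPRS effect size, the interview-based coping effect size and the correlation between them. MEMS and record-checked rehospitalization are less exposed.

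The rejection rates of 7%, 14% and 26% at 40 per arm (7%, 12% and 22% at 32) show what modest bias could do at this sample size. They do not predict its size: the shifts, the 1:1 allocation and the dropout are assumptions, and a t-test is not the planned analysis. The gap should be closed because doing so is cheap; it does not undermine the pilot's feasibility aims.

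**What to change.** Add a paragraph on masking to C3, working within the existing RA pool:

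- For each patient, the RA who rates the BPRS, MACS-II, BARS and THI-4 at months 1, 2 and 4 has no part in that patient's app set-up, app support, prompting, app-data review or provider reports, and cannot see the allocation in REDCap.
- That RA does not carry out the patient's outpatient-record cross-check before the BPRS is locked. MACS-only reports go to those outpatient clinicians (C3, MACS communication with outpatient providers), so the records may reveal the arm.
- At every visit the BPRS is completed and locked before any app questionnaire or feedback interview, and other staff run the feedback interview.
- Patients are asked not to discuss app content with the rater. Any unmasking, and the rater's guess of arm, are recorded and reported.
- If there are too few RAs for full separation, keep at least the BPRS-first order and the recording of unmasking, and report the ratings as unmasked.

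The cost is a protocol paragraph and less flexible RA scheduling. The protocol refers to several RAs and allows assessment by phone or video, which helps. It does not state how many RAs there are, so whether full separation is possible without extra staff needs to be confirmed.
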